IRB Application for Population Health and Quality Research Study

Title of Study: rhBMP-2 versus Vivigen, a novel cellular allograft, in lumbar fusion procedures: a prospective randomized controlled study

Background and Statement of Context

Instrumented lumbar fusion procedures with bone graft are one of the most common procedures performed today. There are numerous bone graft options, including iliac crest bone graft, local autograft, allograft, extenders, and rhBMP [1]. Several studies have demonstrated the efficacy and complications associated with these bone graft options [2-6]. Iliac crest autograft, long considered the gold standard of bone graft, is associated with donor site morbidity, longer operative times, and limited availability [7]. Recombinant human bone morphogenetic protein-2 (Infuse) has revolutionized lumbar fusion surgery. Initially approved for a single level ALIF, Infuse has been utilized in many off-label applications. Further studies of Infuse demonstrated multiple adverse effects, such as osteolysis, ectopic bone formation, retrograde ejaculation, and potentially carcinogenesis [8]. The premium cost and adverse effects of Infuse has led researchers to develop other options. A novel bone graft option is the cellular allograft, a cryopreserved mixture of viable bone cells, demineralized bone matrix, and cancellous bone chips. This product is purported to be osteogenic, osteoinductive, and osteoconductive. There is a paucity of literature evaluating these cellular allograft bone graft options in lumbar spine surgery. This study is aimed at comparing the overall efficacy (clinical and radiographic) of Vivigen, a novel cellular allograft product, and rhBMP-2 when utilized in lumbar fusion procedures.

Study Questions/Objectives and Hypothesis

The purpose of this study is to compare the overall efficacy (clinical outcome and radiographic fusion) of Vivigen (cellular allograft product) and rhBMP-2 in patients who undergo a single level lumbar instrumented fusion. Specifically, when compared to their control group counterparts treated to rhBMP-2, we hypothesize that the intervention group administered Vivigen would, following surgery, experience:

1. Comparable mean postoperative leg/back pain score, where the pain scores are obtained using the numeric rating scale of 0-no pain, to 10-worst pain possible
2. Comparable inpatient length of stay (LOS)
3. Comparable postoperative Oswestry Disability Index (ODI) score (0-no disability, to 100-maximum disability possible), two weeks, 6 weeks, 3 months, 6 months, and 1 year postoperatively
4. Comparable fusion rates, evaluated via CT scan 1 year postoperatively

Study Benefits to Virtua

Virtua could stand to gain some significant cost savings if the more cost-effective Vivigen is shown to be a clinically equivalent bone graft option that can replace the more expensive rhBMP-2.

Study Methodology

Patients who meet all of the following inclusion criteria may be eligible to participate in the study if:

1. Age 18 or older;
2. Diagnosed with lumbar degenerative/isthmic spondylolisthesis, degenerative disc disease with axial low back pain and neurologic symptoms, failed conservative treatment and eligible for a single level lumbar instrumented fusion;
3. Willing to provide informed consent, participate in study, and comply with study protocol.

Patients who meet any of the following criteria may not be eligible to participate:

1. Pregnant or contemplating pregnancy prior to surgery;
2. Serious spinal conditions (e.g. spinal cord compression, cauda equina syndrome, spinal infection, spinal tumor, spinal fracture, inflammatory or systemic spinal arthritis);
3. Surgery involving more than 2 vertebral levels;
4. Worker's compensation or personal injury related to lumbar spine (treatment outcomes may be affected by patient's personal interests; could also run into potential issues with reimbursement).
5. Lactating women
6. Patients who have a known or suspected allergy to Gentamicin Sulfate, Meropenem, Vancomycin, Dimethyl Sulfoxide (DMSO), and Human Serum Albumin
7. Immune compromised patients

During the preoperative office visit, the surgeon will inform patients that appear to meet study eligibility criteria, about the study, and discuss the differences between the two bone graft options, including their potential risks and benefits. The surgeon will make clear to the patient that consenting to be a part of the study means that the patient has agreed to be randomly assigned to one of the two bone graft groups.

Patients who are deemed eligible to participate in the study and are willing to participate will be asked by a trained study physician assistant (PA) to complete the research informed consent. This document will be summarized verbally by the PA and potential participants will be given the opportunity to ask questions about the protocol or their involvement prior to providing consent. Those who agree to

participate and provide research informed consent will be enrolled in the study, and given a copy of the research informed consent document. The patient's informed consent would be added to the patient's chart.

A computer generated randomization scheme will be employed and the randomization outcomes will be sealed in envelopes. On the day of surgery, in the operating room, the circulating nurse will pick an envelope from the randomized stack, unseal the envelope, and based on the outcome (even or odd), assign the patient to one of the two bone graft groups. While the study intervention group (even) will receive 5cc Vivigen and local autograft, the control group (odd) will receive small kit rhBMP-2 with local autograft. Anesthesiologists will use their usual pre-operative and intra-operative techniques for all study participants.

The surgical team, including the surgeons, will be blinded to the treatment options until decompression/instrumentation have been completed. The patients and all staff, including hospital nursing staff, case management, and physical therapists, will be blinded as to which bone graft treatment the patient received.

The primary outcome in this study will be the mean Oswestry Disability Index (ODI) score. The ODI is one of the most commonly utilized condition-specific measures of disability used in the management of spinal disorders [9]. The ODI Version 2.0 is what the Virtua Memorial Spine Center currently uses to examine patient disability preoperatively, as well as two weeks, 6 weeks, 3 months, 6 months, and 1 year postoperatively. The ODI has 10 sections of six statements with the first statement corresponding to a score of 0 indicating no disability and the last statement corresponding to a score of 5 indicating maximum possible disability. The final score which is calculated as: $[\text{total score}/(5 \times \text{number of questions answered})] \times 100\%$, could range from 0% to 100% [9].

Adopting a standard deviation of 10, which is one of the most commonly used standard deviations in ODI studies [9], and looking to detect a mean difference of 8 in ODI scores to indicate superiority of one bone graft option over the other, it is estimated that for a statistical power of 80% and significance level of 0.05, a minimum of 26 participants will be required in each study group for a total of 52 study participants. To minimize the possibility of dropouts or incomplete data impacting the analysis, a minimum of 30 participants will be enrolled in each study group, for a total of 60 study participants.

Secondary outcome measures in this study include the mean scores from the 36-Item Short Form Survey Instrument (SF-36) [10]; the mean leg/back pain scores from the numeric rating scale of 0-no pain, to 10-worst pain possible; mean LOS; incidence of ORAEs, and fusion rates examined via CT scan 1 year postoperatively by an independent radiologist.

Means will be compared between the two study groups using one-tailed 2-sample t tests, proportions will be compared using chi-square tests, and logistic regression will be used to analyze for confounding effects. All statistical analyses will be conducted in Minitab 16 Statistical Software.

Protection of Human Subjects

Throughout the study, the principal investigators (Virtua Memorial spine surgeons and PAs), will be the only ones with access to the data collection database. Following the completion of the study, all personal health information collected, including name, gender, age, significant medical comorbidities, and postoperative complications, will be de-identified as soon as possible prior to data analysis and any subsequent publications or research submissions. Patient would be told participation is purely voluntary with no monetary reimbursement and minimal risk of being assigned to one of the two pain management groups.

References

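### Consider excluding active cancer at any site: the protocol names potential carcinogenesis for rhBMP-2, but its only tumour exclusion is limited to the spine

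*Combined protocol and SAP*

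**What the plan says.** - **Hazard.** In Background and Statement of Context: "Further studies of Infuse demonstrated multiple adverse effects, such as osteolysis, ectopic bone formation, retrograde ejaculation, and potentially carcinogenesis [8". Infuse is the rhBMP-2 product.
- **Exposure.** Study Methodology gives rhBMP-2 with local autograft to every patient randomised to the control group. The circulating nurse opens the envelope in the operating room, and the surgeons do not know the graft until the decompression and instrumentation are done.
- **Exclusions.** There are seven, introduced by "Patients who meet any of the following criteria may not be eligible to participate". Item 2 holds the only tumour term: "Serious spinal conditions (e.g. spinal cord compression, cauda equina syndrome, spinal infection, spinal tumor, spinal fracture, inflammatory or systemic spinal arthritis". Item 6 reads "Patients who have a known or suspected allergy to Gentamicin Sulfate, Meropenem, Vancomycin, Dimethyl Sulfoxide (DMSO), and Human Serum Albumin" and item 7 reads "Immune compromised patients". The others cover pregnancy, surgery on more than two levels, compensation or injury claims, and lactation.
- **Inclusions.** There are three. Item 2 ends "failed conservative treatment and eligible for a single level lumbar instrumented fusion". None mentions cancer, and age has no upper limit.
- **Steps before consent.** "During the preoperative office visit, the surgeon will inform patients that appear to meet study eligibility criteria, about the study"; in the same conversation the surgeon covers how the grafts differ and the risks and benefits of each. "Patients who are deemed eligible to participate in the study and are willing to participate" then go to a trained physician assistant, who summarises the consent form and takes questions.

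**The concern.** The protocol itself raises a possible link between one of its two grafts and cancer. Its written criteria then address tumours only as a disease of the spine. They are silent on the patient who has active cancer elsewhere and is otherwise a sound candidate for fusion.

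The design makes screening the natural place for this decision. A consenting patient has agreed to random assignment, the graft is revealed in theatre, and the visible text describes no later step at which the graft is matched to the patient's history. If the question is not settled before consent, each surgeon settles it informally, and like patients may be handled differently.

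Patient safety and consistent enrolment are at stake. The validity of the Oswestry Disability Index (ODI) comparison is not: eligibility is decided before randomisation, so both arms are drawn from the same population with or without the added criterion.

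**Working it through.** **1. Exclusion items read against the case.** Take a patient with active cancer outside the spine who is not immune compromised, and who is otherwise suitable.

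| Item | Subject | Excludes this patient? |
|---|---|---|
| 1 | Pregnancy | No |
| 2 | Serious spinal conditions, with spinal tumour as an example | No, the cancer is not spinal |
| 3 | More than two levels | No |
| 4 | Compensation or injury claim | No |
| 5 | Lactation | No |
| 6 | Allergy to listed agents | No |
| 7 | Immune compromised | No, by construction |

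Item 7 may catch some patients under cancer treatment, but not all patients with active cancer.

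**2. Counts.**
- Exclusions with a tumour term: 1 of 7.
- Exclusions with a tumour term that reaches beyond the spine: 0 of 7.
- Inclusions that mention cancer: 0 of 3.
- Exclusions that can be read as safety criteria unrelated to spinal disease: 4 of 7 (items 1, 5, 6 and 7). This last count is an interpretation, because the protocol gives a reason only for item 4.

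**3. Other safeguards.** Inclusion item 2 asks whether the patient is eligible for fusion, which is not the same as suitability for rhBMP-2. The surgeon's discussion and the consent summary inform the patient, who may decline. Neither is a rule about whom to enrol, and none of the three mentions cancer in the visible text.

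**4. Does the change disturb the sample size?** The plan's inputs are SD 10, difference 8, power 80% and significance level 0.05.

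- Normal approximation, two-sided: n = 2 × (1.960 + 0.842)² × 10² / 8² = 24.5, rounded up to 25 per group.
- Two-sample t test, two-sided: 25.52, rounded up to 26 per group. This reproduces the plan's figure.
- Power of the two-sided t test: 80.7% at 26 per group and 86.1% at 30 per group.

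None of these inputs refers to who is excluded, so the plan's 52 (60 with the dropout allowance) stands, provided the SD of 10 still applies.

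**5. Effect on recruitment.** The documents do not say how many candidates have active cancer. Let *p* be the share of otherwise eligible patients excluded. The number to screen for 60 enrolled is 60 / (1 − *p*), rounded up:

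| Assumed *p* | Number to screen |
|---|---|
| 1% | 61 |
| 3% | 62 |
| 5% | 64 |
| 10% | 67 |

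The values of *p* are assumptions that show a range; they are not estimates.

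**The case against.** The strongest objection is that hazard and remedy do not match. The Background speaks of causing cancer; the proposed exclusion concerns patients who already have it. A reader might infer that rhBMP-2 is known to be harmful in such patients, or that the exclusion would lower the carcinogenic risk in the trial. The documents support neither. They do not say that rhBMP-2 worsens an existing tumour, and the exclusion does nothing for patients without cancer. This part of the objection stands and limits the point to precaution.

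A reader might also infer that only the surgeon's discretion keeps such a patient out of the rhBMP-2 arm. That is too strong. The risks of each graft are discussed before consent, the physician assistant goes over the form and answers questions, and the patient can refuse. These are real safeguards, though they inform rather than screen.

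Two smaller objections also stand. The counts describe wording, not risk. And active malignancy needs a working definition for localised skin cancers and long-term maintenance therapy.

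Finally, the consent pages were removed and the only appendix shown is numbered 3, so an equivalent criterion elsewhere cannot be ruled out. The eligibility list itself looks complete.

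None of this changes what the list says: the protocol names a cancer concern for one graft, and its criteria do not address patients with active cancer outside the spine.

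**Conclusion.** The point holds as a cheap, precautionary improvement to patient safety, to be considered by the sponsor's clinicians. As written, the visible criteria allow a patient with active non-spinal cancer who is not immune compromised to be randomised to a graft for which the protocol itself names potential carcinogenesis.

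Its size cannot be expressed as harm: no frequency and no harm rate can be derived from the documents. It is not a statistical error, and no effect on power or on the ODI comparison is claimed.

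The conclusion rests on two assumptions: that the visible list is the full set of criteria, and that a named, potential cancer concern is reason enough to decide explicitly about patients who already have cancer.

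**What to change.** Add one item to the exclusion criteria under Study Methodology: *known active malignancy at any site, including current cancer treatment*. Apply it to every candidate at the preoperative visit, before consent and randomisation and regardless of arm. The sponsor's clinicians should decide, and write down, how to treat localised skin cancers, long-term maintenance therapy and past cancer. If an equivalent criterion exists on pages not shown, confirming that is enough.

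The cost is a short amendment, a working definition, and one question at a visit that already takes place. Protection of Human Subjects lists significant medical comorbidities among the data collected, but that sentence concerns de-identification and does not describe screening, so the question should be added explicitly. The eligible pool becomes somewhat smaller by an amount the documents do not give. The enrolment target of 60 and the planned analysis stay as they are.

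### Surgeon and fusion approach are controlled neither in the allocation as described nor in the ODI analysis; recording both and adjusting for them in a linear model is a cheap gain

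*Combined protocol and SAP*

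**What the plan says.** The Study Methodology section is the only account of allocation. It states that "A computer generated randomization scheme will be employed and the randomization outcomes will be sealed in envelopes". At operation, "the circulating nurse will pick an envelope from the randomized stack, unseal the envelope". The rule for reading the envelope is that staff, "based on the outcome (even or odd), assign the patient to one of the two bone graft groups". Only one stack is described. The type of scheme, any blocking and any strata are not given.

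Eligibility asks that the patient be "eligible for a single level lumbar instrumented fusion", for spondylolisthesis or degenerative disc disease. No approach is fixed. Protection of Human Subjects lists the principal investigators as "Virtua Memorial spine surgeons and PAs", so there is more than one surgeon. Their number and caseloads are not stated.

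The sample-size paragraph specifies "a minimum of 30 participants will be enrolled in each study group, for a total of 60 study participants". The analysis paragraph compares means by one-tailed two-sample t tests and proportions by chi-square tests. It assigns confounding to logistic regression and names neither outcomes nor covariates.

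**The concern.** Surgeon and approach are natural candidates to influence disability, length of stay and CT fusion whichever graft is used. The Background also notes that the control graft's regulatory status differs by approach: "Initially approved for a single level ALIF, Infuse has been utilized in many off-label applications".

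A small trial can handle such factors by balancing them at allocation or by adjusting for them in the analysis. As written, this plan does neither for its primary outcome. Logistic regression needs a binary outcome. It could serve for fusion (yes/no), but not for mean ODI unless ODI is dichotomised, which the plan does not propose. If the single allocation obtained is uneven on approach or surgeon, the ODI comparison carries that unevenness and no planned analysis removes it.

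**Working it through.** **Inputs from the protocol.** SD of ODI 10, target difference 8, power 80%, alpha 0.05, 26 per group required and 30 per group enrolled (all from the sample-size paragraph).

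**Assumptions.** The protocol gives neither the mix of approaches or surgeons nor their effect on ODI. I take a two-level factor with prevalence 20% to 50% and an ODI effect of 4 to 8 points.

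**1. The plan's own figure.** A two-sided t-based calculation for a difference of 8 with SD 10 gives 25.5, so 26 per group (power 80.8%). The stated 26 is reproduced. With 30 per group the power is 86.1%.

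**2. Chance of a sizeable imbalance.** Let K of the 60 patients have the factor and let X be the number of them in the Vivigen arm. With 30 per arm fixed, X follows Hypergeometric(60, K, 30). The gap between arms is |2X − K|/30, so a gap of at least 20 percentage points means |2X − K| ≥ 6.

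| Assumed prevalence | K | P(gap ≥ 20 points) | P(gap ≥ 30 points) |
|---|---|---|---|
| 20% | 12 | 10.4% | 0.2% |
| 30% | 18 | 15.8% | 1.0% |
| 40% | 24 | 18.7% | 1.7% |
| 50% | 30 | 19.6% | 1.9% |

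**3. Shift in the graft difference.** Shift = gap × factor effect.
- For a 20-point gap: 0.20 × 4 = 0.8 points, or 0.20 × 8 = 1.6 points. These are one tenth and one fifth of the 8-point target.
- On average over allocations at 50% prevalence, the mean absolute gap is 0.102. The mean absolute shift is therefore 0.102 × 8 ≈ 0.8 points for an 8-point factor and 0.102 × 4 ≈ 0.4 for a 4-point factor.
- The standard error of the comparison is 10 × √(2/30) = 2.6 points.

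**4. Error rate.** I used simulation with 40,000 trials per scenario, 50/50 prevalence, total SD 10 and no graft effect.

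| Unadjusted t test | Factor effect 4 | Factor effect 8 |
|---|---|---|
| All trials, two-sided | 5.0% | 5.0% |
| Trials with gap ≥ 20 points, two-sided | 5.7% | 9.2% |
| Same gap in the tested direction, one-tailed | 8.9% | 15.5% |

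In the trials with a gap of at least 20 points, a linear model containing the factor brings the two-sided error back to 4.6% to 4.7%.

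**5. Precision.** With a 50/50 factor, the residual SD after adjustment is √(100 − 0.25 × d²), where d is the factor effect.
- d = 8: √84 = 9.2. Simulated two-sided power for an 8-point graft difference rises from about 86% to about 91% with adjustment alone, and to about 92% with stratified allocation as well.
- d = 4: √96 = 9.8. Power moves from about 86% to 87%, which is almost no gain.

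**The case against.** The strongest reply is that randomisation already deals with this. The error rate of the t test covers chance imbalance, and the overall figure of 5.0% confirms it. That stands. A reader might infer that an uneven draw could pass for a graft effect, or that false-positive findings are generally more likely. The figures do not support this: the raised error rates apply only to an uneven draw, and a shift of 0.8 to 1.6 points cannot by itself produce an 8-point difference.

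The absence of strata is also inferred from silence, since the protocol does not describe the scheme. The mix of approaches is not reported, and nothing in the protocol says that surgeon or approach affects ODI. The sentence about ALIF is regulatory history and gives no evidence on prognosis. These points stand too, which is why the effect sizes above are labelled as assumptions.

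A reader might further take the even/odd label to mean coin-toss allocation that could miss the planned arm sizes. The text does not support that. Even and odd are only what the envelope shows, and the sample-size paragraph specifies 30 per group, which fits a prepared balanced stack.

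Finally, stratifying in short blocks has a cost. Surgeons introduce the study to patients and learn the graft once decompression and instrumentation are complete. In a simulated stratum of 30 with blocks of 2 and 4, guessing the under-represented arm is right about 72% of the time, against about 57% for one shuffled stack of 60. This argues against short blocks. It does not touch adjustment in the analysis, which recovers nearly all of the benefit.

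**Conclusion.** The point holds in a limited form. Neither the allocation as described nor the ODI analysis accounts for approach or surgeon, and the one adjustment method named does not fit the primary outcome. The cost is bias conditional on an uneven draw, together with some lost precision. The overall error rate and the validity of the randomisation are not in question.

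The size depends on assumptions the protocol cannot settle. If neither factor affects ODI, nothing is lost; at an effect of 4 points the loss is small; at 8 points adjustment is worth about five percentage points of power. The change is worth making because it is cheap, not because the trial fails without it.

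**What to change.** 1. Record the intended approach and the operating surgeon for every patient before the envelope is opened, so that neither can be influenced by the allocation.
2. Replace the unadjusted ODI t test with a prespecified linear model containing graft group and approach, plus surgeon if there are few surgeons. Keep logistic regression for binary outcomes such as fusion, and name its covariates.
3. State the type of randomisation scheme.
4. Optionally, prepare a separate balanced envelope set for each approach. Use larger blocks of varying size rather than 2 and 4, because the surgeons who recruit also learn past allocations. If allocation is stratified, the model must include the stratum: with an 8-point factor, stratifying without adjusting gives a conservative test, with two-sided error about 3.2%.

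The cost is one degree of freedom per added term (a two-level approach leaves 57 instead of 58 with 60 patients) and two extra items to record. The required sample size does not rise. Stratifying would add a second envelope set and make allocation somewhat more predictable.

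### The primary outcome is mean ODI with no visit named, although ODI is scheduled at five postoperative visits and the trial is sized for one comparison at 0.05

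*Combined protocol and SAP*

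**What the plan says.** The primary outcome is defined in the Study Methodology section: "The primary outcome in this study will be the mean Oswestry Disability Index (ODI) score". The text then describes the questionnaire and its scoring, and reports that the centre's version is what it "currently uses to examine patient disability preoperatively, as well as two weeks, 6 weeks, 3 months, 6 months, and 1 year postoperatively". Item 3 of Study Questions/Objectives and Hypothesis predicts comparable ODI at the same five postoperative times and singles out none of them.

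The sample-size paragraph takes an SD of 10 and is "looking to detect a mean difference of 8 in ODI scores to indicate superiority of one bone graft option over the other". It concludes that "for a statistical power of 80% and significance level of 0.05, a minimum of 26 participants will be required in each study group", and enrolment is raised to 30 per group for dropout. Neither the SD nor the difference is tied to a visit.

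The analysis paragraph says: "Means will be compared between the two study groups using one-tailed 2-sample t tests". It adds chi-square tests for proportions, and that "logistic regression will be used to analyze for confounding effects". It contains no repeated-measures model, across-visit average, change-from-baseline definition or multiplicity rule. CT fusion, a secondary outcome, is the one efficacy outcome that is tied to a single visit (1 year).

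**The concern.** The plan fixes the instrument, the contrast (a difference in group means), the type of test and one effect size. It does not fix which ODI measurement enters the primary comparison. Someone following it would have five postoperative ODI comparisons, each testable at 0.05, and nothing written beforehand to say which one is the trial's result.

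The sample-size paragraph looks for superiority of either graft. With the visit left open, a significant result at any of five times could be presented as the primary finding, and the 0.05 in the sample-size paragraph would no longer describe the chance of a false claim. The stated benefit is a possible replacement of one graft by a cheaper one, so readers need to know which comparison was meant to settle the question.

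**Working it through.** **Inputs from the documents (Study Methodology).** Difference 8, SD 10, power 80%, significance level 0.05, 26 per group, five postoperative ODI visits. **Assumed, because the documents give no value:** a between-visit correlation ρ of 0.3 to 0.9, equal for all pairs of visits unless stated.

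**1. Reproducing 26 per group.** For a two-sample t test with n = 26 per group:
- standard error = 10 × √(2/26) = 2.77
- noncentrality = 8 / 2.77 = 2.88, with 50 degrees of freedom
- two-sided power = 80.7%; at n = 25 it is 79.1%

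The exact two-sided solution is 25.52, which rounds up to 26. The one-sided solution is 20.03, or 21 per group, so 26 corresponds to one two-sided test. The arithmetic is correct, and it covers one comparison.

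**2. False-positive rate if any of five visits may be cited.** If the five tests were independent: 1 − 0.95⁵ = 0.226. Correlated visits were simulated at patient level (26 per group, SD 10 at each visit, no true difference, pooled t tests at 0.05, 60,000 replicates per cell):

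| Assumed ρ | Two-sided | One-tailed, same direction at every visit |
|---|---|---|
| 0.3 | 21.4% | 19.7% |
| 0.5 | 18.5% | 16.6% |
| 0.7 | 14.8% | 13.3% |
| 0.9 | 10.2% | 9.6% |
| One named visit | 5% | 5% |

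A separate normal-theory simulation gave 20.9%, 18.3%, 14.8% and 10.2% two-sided, and 19.3% to 9.4% one-tailed, so the two agree to within about half a percentage point. If the correlation decays with the gap between visits (ρ raised to the power of the visit lag), the two-sided range is 21.6% to 11.8%.

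**3. If all five visits were meant to be primary, with success at any one.** A Bonferroni level of 0.05/5 = 0.01 needs 39 per group (two-sided t test). The planned 30 per group gives 67% power at that level, and 26 gives 58%.

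**4. If an average over the five visits was meant.** With SD 10 at each visit, the SD of the average is 10 × √((1 + 4ρ)/5):
- ρ = 0.3: 10 × √(2.2/5) = 6.6
- ρ = 0.9: 10 × √(4.6/5) = 9.6

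The SD of 10 would then not be the right input.

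**5. Power after naming one visit.** A plain two-sided t test at that visit keeps 80.7% if SD 10 and difference 8 apply there. Adjustment for preoperative ODI, simulated at 26 per group, gives about 80%, 84% and 90% for assumed correlations of 0, 0.3 and 0.5 between preoperative and follow-up ODI. If the SD at the chosen visit were 12 or 15, the two-sided t test would need 37 or 57 per group.

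**The case against.** **The false-positive figures assume selective citation.** The plan nowhere says that one significant visit is enough for success. This stands. The 21% to 10% describes what the wording leaves open, not what the investigators intend or would do.

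**One year, or an average, may be implied.** Neither can be shown from the text. Hypothesis 3 gives the five visits equal standing. The analysis paragraph uses the word mean for group means, and length of stay, which has one value per patient, is also described by its mean.

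**A reader might infer a matching inflation on the comparable side.** The argument would be that, with a true difference of 8 at every visit, at least one of five visits is often non-significant and could be cited as showing comparability. The documents do not support this as a consequence of the missing visit:
- Hypothesis 3 can be read as requiring comparability at all five visits. Under a constant difference of 8, SD 10, 26 per group and ρ of 0.3 to 0.9, all five two-sided tests are non-significant in only about 0.7% to 10% of trials. That is below the 19% (100% − 80.7%) for one named visit, so the direction reverses.
- No passage supports a constant difference from two weeks to 1 year.
- Treating non-significance as comparability is unsound at any visit, named or not. It belongs to the separate conflict between a superiority calculation and the aim that Vivigen be shown "if the more cost-effective Vivigen is shown to be a clinically equivalent bone graft option".

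**Baseline adjustment goes beyond the defect.** In part this is right: a plain t test at a named visit would close the gap. Adjustment is recommended on efficiency grounds only.

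**Conclusion.** The concern holds as an omission in the definition of the primary comparison. The documents name no deciding visit, no across-visit summary and no multiplicity rule, while the sample size covers exactly one two-sided comparison. If any significant visit could be cited, the false-positive rate could reach about 21% to 10% two-sided, or about 20% to 9% one-tailed with one direction fixed for all visits, against the stated 5%. These figures rest on assumed correlations of 0.3 to 0.9, on SD 10 at every visit and on free choice among five visits; they are a ceiling.

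The finding does not show that 26 per group is miscalculated, nor that the investigators plan to choose a visit after seeing results. The one-tailed versus two-sided mismatch and the superiority versus comparable conflict are separate points.

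**What to change.** Before any outcome is analysed, state one primary comparison. Suggested text:

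> The primary endpoint is the between-group difference in mean ODI at 1 year, adjusted for preoperative ODI; ODI at 2 weeks, 6 weeks, 3 months and 6 months is secondary and reported as estimates with confidence intervals.

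One year is proposed because it is the last scheduled visit. The documents do not rank visits, so the investigators should confirm or replace it.

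- **Analysis paragraph.** Name the adjusted comparison, since only t tests, chi-square tests and logistic regression are listed now. State that preoperative ODI is collected as study data: it is described as part of the centre's current practice, while hypothesis 3 lists postoperative scores only. If the investigators prefer, an unadjusted t test at the named visit also settles the point.
- **Sample-size paragraph.** State that SD 10 and difference 8 refer to the chosen visit. If they do, 26 per group can stay; if not, recalculate.
- **If a five-visit average is preferred.** Restate the SD (about 6.6 to 9.6 under the assumptions above) and the basis of the sample size.

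The cost is a few sentences and no extra assessments. Adjustment loses less than one percentage point of power if preoperative and 1-year ODI are uncorrelated, and gains power otherwise. The real price is that differences at early visits become supportive only. This change does not settle the sidedness of the test or the superiority versus comparable question.
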